4.2 Determination of Sample Size

Not applicable for the 5 to 7-year follow-up.

5 DATA SETS TO BE ANALYSED

The following analysis sets will be used for the statistical analysis and presentation of data:

The **Safety Set** will consist of patients who:

- were included in the Safety Set in the Clinical Study Reports Addendum dated 11 August 2015 for the 3 year follow-up visit
- have at least one assessment at the 5-7-year follow-up visit

The **Intention-to-Treat (ITT)** set will consist of patients who:

- were included in the ITT in the Clinical Study Reports Addendum dated 11 August 2015 for the 3 year follow-up visit
- have at least one assessment of the efficacy variable mGFR or [REDACTED] at the 5-7-year follow-up visit

The **Per Protocol Set (PPS)** will consist of patients who:

- were included in the PPS in the Clinical Study Reports Addendum dated 11 August 2015 for the 3 year follow-up visit
- have at least one assessment of the efficacy variable mGFR or [REDACTED] at the 5-7-year follow-up visit
- are on their randomized treatment according to the CRF-page *Immunosuppressive Medications* i.e. Everolimus (without addition of CsA or Tacrolimus) or Control (Control=CsA and/or Tacrolimus without addition of Everolimus) at the 5-7-year follow-up visit
- have no major protocol deviation at the 5-7-year follow-up visit. The final criteria for PPS, regarding which protocol deviations that warrant exclusions, will be determined when all data on protocol deviations are available and will be documented in a separate document before database lock

The **Extended PPS** will consist of patients who:

- were included in the ITT in the Clinical Study Reports Addendum dated 11 August 2015 for the 3 year follow-up visit
- have at least one assessment of the efficacy variable mGFR or [REDACTED] at the 5-7-year follow-up visit
- are on their randomized treatment according to the CRF-page *Immunosuppressive Medications* i.e. Everolimus (Everolimus=Everolimus or Everolimus and CsA and/or Tacrolimus) or Control (Control= CsA and/or Tacrolimus without addition of Everolimus) at the 5-7-year follow-up visit
- have no major protocol deviation at the 5-7-year follow-up visit. The final criteria for PPS, regarding which protocol deviations that warrant exclusions, will be determined when all data on protocol deviations are available and will be documented in a separate document before database lock

The ITT is considered as the primary analysis dataset, and will be used for the primary, secondary [REDACTED] variables. The primary efficacy analysis will be repeated using the PPS and extended PPS.

Demographic presentations will be based on the safety set and on the ITT. Exposure to treatment presentations will be based on safety set, ITT, PPS and extended PPS.

Safety presentations will be based on the safety set.

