4.4 Statistics

The primary efficacy analysis will be based on the intention-to-treat (ITT) population. Statistical hypothesis testing will be performed, and confidence interval (CI) will be derived to estimate the effects. Two-sided tests will be performed on the 5% level of significance, and 95% two-sided CI for least square mean will be presented.

The null hypothesis is that there is no difference in the mean of mGFR between the everolimus arm ($\mu_{\text{Everolimus}}$) and the control arm (Control) (μ_{Control}) and the alternative hypothesis is that there is a difference between everolimus and control at the 5 to 7-years follow-up visit.

$$H_0: \mu_{\text{Everolimus}} - \mu_{\text{Control}} = 0$$

$$H_1: \mu_{\text{Everolimus}} - \mu_{\text{Control}} \neq 0$$

The above between-group comparisons will be performed using an ANCOVA with study treatment (Everolimus, Control) and randomization strata (mGFR above/below 60 mL/min and have/not have mechanical assist device) as classification variables. In addition, the mGFR values at baseline (Visit 6) will be used as covariate.

In general data will be summarised by means of summary statistics. For continuous data, the following summary statistics will be presented: number of observations, mean value, standard deviation, minimum, first quartile, median, third quartile and maximum value. Categorical data will be presented as counts and percentages. Summary statistics will be presented by treatment group/total and assessment visit, as applicable. Individual patient data will be listed.

The analyses of the data from the 5 to 7-year follow-up visit will be presented in a statistical analysis plan (SAP) prepared prior to database lock.

Data sets to be analysed:

The Safety Set will consist of patients who:

- were included in the Safety Set in the Clinical Study Reports Addendum dated 11 August 2015 for the 3 year follow-up visit
- have at least one assessment at the 5 to 7-year follow-up visit

The Intention-to-Treat (ITT) set will consist of patients who:

- were included in the ITT in the Clinical Study Reports Addendum dated 11 August 2015 for the 3 year follow-up visit
- have at least assessment of the efficacy variable mGFR [REDACTED] at the 5 to 7-year follow-up visit

The Per Protocol Set (PPS) will consist of patients who:

- were included in the PPS in the Clinical Study Reports Addendum dated 11 August 2015 for the 3 year follow-up visit

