4.5 Adverse Events

4.5.1 Definitions

Adverse Event

Any untoward medical occurrence in a patient or clinical trial patient administered a medicinal product and which does not necessarily have a causal relationship with this treatment.

Comment: An AE can therefore be any unfavourable and unintended sign (including an abnormal laboratory finding), symptom, or disease temporally associated with the use of an investigational medicinal product (IMP), whether or not considered related to the IMP.

Adverse Reaction

All untoward and unintended responses to an IMP related to any dose administered.

Comment: All AEs judged by either the reporting Investigator or the Sponsor as having a reasonable causal relationship to a medicinal product qualify as adverse reactions. The expression reasonable causal relationship means to convey in general that there is evidence or argument to suggest a causal relationship.

Unexpected Adverse Reaction

An adverse reaction, the nature or severity of which is not consistent with the applicable product information (e.g. Investigator's Brochure for an unauthorized IMP or SmPC for an authorized product).

Comments: When the outcome of an adverse reaction in this study is not consistent with the applicable product information, i.e. Section 4.8 of the SmPC, this adverse reaction should be considered as unexpected.

Serious Adverse Event

Any untoward medicinal occurrence or effect that at any dose:

- Results in death
- Is life-threatening
- Requires hospitalization or prolongation of existing hospitalization
- Results in persistent or significant disability or incapacity
- Is a congenital anomaly or birth defect

Comments: Life-threatening in the definition of a serious adverse event (SAE) or serious adverse reaction refers to an event in which the patient was at risk of death at the time of event; it does not refer to an event which hypothetically might have caused death if it was more severe.

Medical judgment should be exercised in deciding whether an AE/reaction is serious in other situations. Important AEs/reactions that are not immediately life-threatening or do not result in

[figure not shown]
death or hospitalization but may jeopardize the patient or may require intervention to prevent one of the other outcomes listed in the definition above, should also be considered serious.

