4.5.2 Occurrence of Selected Adverse Events (Including Serious Adverse Events) – Main Categories

AEs considered clinically relevant are listed in Table 2. Any of these AEs that have occurred during the time between the 3-year follow-up visit and the 5 to 7-year follow-up visit should be registered in the case report form (CRF).

All SAEs should be reported to Novartis on specific SAE forms within 24 hours of learning of its occurrence to:

Clinical Safety Desk Fax:

To be answered: Has there been any occurrences of (clinically relevant) AEs since the 3-year follow-up visit i.e. from the 3-year follow-up visit to the 5 to 7-year follow-up visit.

The total number of each AE/SAE should be recorded, i.e. one patient may have experienced several AEs. Further details regarding collection and handling of AEs/SAEs are provided in Appendix 1.

• **Table 2 Selected Adverse Events – Main Categories**

Adverse Event	3 years to 5/7 years	
	AE	SAE
Infection		
Pneumonia		
Herpes Zoster		
Herpes simplex		
Sepsis		
Cancer		
Squamous cell carcinoma		
Basal cell carcinoma		
Other skin cancer		
PTLD		
Solid tumor		
Bone marrow toxicity		
Thrombocytopenia (<100000/ μ L)		
Leucopenia (<3500/ μ L)		
Anemia (<10 g/dL)		
Tromboembolic event		
DVT		
Pulmonary emboli		
Stroke/TIA		
Gastrointestinal system		
Diarrhea		
Constipation		
Pain		
Skin		
Rash		
Acne		
Hirsutism		
Cardiac		
Cellular rejection (grade)		
Humoral rejection		
LV dysfunction (EF<30%, or 25%↓)		
Arrhythmias (clinically significant, requiring treatment)		
PCI		
Myocardial infarction		

Adverse Event	3 years to 5/7 years	
	AE	SAE
Renal		
Proteinuria (albumin/creatinine >100)		
Hyperuricemia		
Peripheral oedema		
Gingival hyperplasia		
Other		

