6.3.10 Adverse Events

AEs and SAEs will be coded according to the Medical Dictionary for Regulatory Activities (MedDRA) system and tabulated by System Organ Class (SOC) and by preferred term for the 5-7-years follow-up visit.

The total number of patients with at least one AE and the total number of AEs will be presented by treatment group and in total. AEs with the same preferred term will be counted only once within a patient. The SAEs will be presented in the same way as the AEs.

The safety set will be used for these presentations.

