14.3 SAFETY DATA

(Safety presentations will be based on the Safety set if not other is stated below)

- 14.3.1.x Summary of Adverse Events
- 14.3.1.x Adverse Events by System Organ Class and Preferred term
- 14.3.1.x Summary of Serious Adverse Events
- 14.3.1.x Serious Adverse Events by System Organ Class and Preferred term
- 14.3.2 Listings of Deaths, Other Serious and Significant Adverse Events
- (14.3.3 *this title is reserved for narratives*)
- 14.3.4.x Abnormal Laboratory Value Listing (low and high, if reference values available)
- 14.3.4.x Other Relevant Laboratory Analyses:
 - Clinical chemistry/Biochemistry (summary statistics for observed values and change from baseline by treatment group and total values)
 - Lipid profile (summary statistics for observed values and change from baseline by treatment group and total values)
 - Hematology (summary statistics for observed values and change from baseline by treatment group and total values)
 - Urinalysis (summary statistics for observed values and change from baseline by treatment group and total values)
 - Shift Tables Clinical chemistry/Biochemistry
 - Shift Tables Lipid profile
 - Shift Tables Hematology
 - Shift Tables Urinalysis
- 14.3.5.x Extent of Exposure (Safety set, ITT, PPS, extended PPS)
 - Ongoing Immunosuppressive Treatments at 5-7-years Follow-Up (frequency table)
 - Dose Rate of Immunosuppressive Treatments from the End of the Main Study to the 5-7-years Follow-Up Visit (summary statistics)
 - Trough Blood Levels at 5-7-years Follow-Up (summary statistics for observed values)
- 14.3.6 Vital signs (summary statistics for observed values and change from pre-transplantation by treatment group and in total)
- 14.3.7.x ECG (summary statistics for observed values)
 - Shift ECG for Type of Rhythm

14.3.8.x Cardiac Rejections (frequency table by treatment group)

- Number of patients with at least one cardiac rejection (grade I-III): cellular, humoral or mixed (for three periods: during the main study, between main study to 3-years follow-up and between 3-years follow-up to 5-7-years follow-up)
- Total number of cardiac rejection grade I-III (cellular, humoral or mixed, for three periods: during the main study, between main study to 3-years follow-up and between 3-years follow-up to 5-7-years follow-up)

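### The Safety Set requires an assessment at the 5-7-year visit, so deaths between the 3-year visit and that assessment drop out of the SAE tables and the death listing

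*SAP*

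**What the plan says.** **Who is in the Safety Set.** SAP section 5 sets two conditions, and both must be met. The patient was in the Safety Set of the 3-year report addendum, and must "have at least one assessment at the 5-7-year follow-up visit". Protocol section 4.4 has the same second condition: "have at least one assessment at the 5 to 7-year follow-up visit". The two documents agree, so this is the intended definition and not a slip in one of them.

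**What the safety window covers.** Protocol section 4.5.2 asks for listed "AEs that have occurred during the time between the 3-year follow-up visit and the 5 to 7-year follow-up visit". Section 4.5.1 gives "Results in death" as the first criterion for a serious adverse event. The number of AEs/SAEs is a named endpoint (protocol section 2, SAP section 3.3).

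**Which outputs use the set.**
- General rule in SAP section 5: "Safety presentations will be based on the safety set".
- AE and SAE tables in SAP section 6.3.10: "The safety set will be used for these presentations".
- SAP Appendix 1, section 14.3: "Safety presentations will be based on the Safety set if not other is stated below". Item 14.3.2, "Listings of Deaths, Other Serious and Significant Adverse Events", names no other population.

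**What is known about patients who do not attend.** Protocol section 4.3.1 collects the reason why consent was not given, and death is one of the listed reasons.

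**The concern.** The window for safety events starts at the 3-year visit, but a patient must reach the end of it to be counted. Death before the visit is the one serious event that guarantees exclusion. As written, listing 14.3.2 can show a death only if it followed a 5-7-year assessment.

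This is a randomised comparison of two long-term regimens. If deaths before the visit are unevenly split, the safety section will not show it, and the arm with more deaths can look better than it is. A reader comparing long-term safety by arm would see only patients who survived to be assessed. The plan foresees such deaths, since it records them as a reason for no consent, but no visible output reports them by arm as a safety result.

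**Working it through.** The documents give no event rate, sample size or power figure for this point, so there is no stated figure to reproduce. The check has two parts.

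**1. Apply the definition to one patient.** Take a patient in the 3-year Safety Set who dies after the 3-year visit and before any assessment at the 5-7-year visit.

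| Step | Source | Result |
|---|---|---|
| Is the death inside the AE/SAE window? | Protocol 4.5.2 | Yes |
| Is it a serious adverse event? | Protocol 4.5.1 | Yes |
| In the 3-year Safety Set? | SAP 5, first condition | Yes |
| Any 5-7-year assessment? | SAP 5, second condition; protocol 4.4 | No, so outside the Safety Set |
| Counted in the AE/SAE tables? | SAP 5 and 6.3.10 | No, neither numerator nor denominator |
| Shown in listing 14.3.2? | SAP Appendix 1, 14.3 | No, the default set applies |

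A patient who dies after at least one 5-7-year assessment stays in the set. The gap concerns only deaths before any assessment, and for those the safety outputs show zero whatever the true number.

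**2. Size the gap.** Inputs:
- Base: 102 patients, the number who took part in the 3-year visit (protocol section 3, SAP section 4.1). This stands in for the size of the 3-year Safety Set, which the documents do not give.
- Time at risk: t = 2, 3 or 4 years, from year 3 to year 5, 6 or 7.
- Annual mortality r: not in the documents. Assumed at 1% to 5%.

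Expected deaths left out = 102 × (1 − (1 − r)^t). For example, r = 1% and t = 2 gives 102 × (1 − 0.99²) = 102 × 0.0199 = 2.0. With r = 5% and t = 4 it is 102 × (1 − 0.95⁴) = 102 × 0.1855 = 18.9.

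| Assumed r per year | t = 2 | t = 3 | t = 4 | Visits split equally over the three years |
|---|---|---|---|---|
| 1% | 2.0 | 3.0 | 4.0 | 3.0 |
| 2% | 4.0 | 6.0 | 7.9 | 6.0 |
| 3% | 6.0 | 8.9 | 11.7 | 8.9 |
| 5% | 9.9 | 14.5 | 18.9 | 14.5 |

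The last column is the mean of the three before it. As a share of 102, the range runs from 2.0% to 18.5%.

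The chance of at least one such death is 1 − (1 − r)^(102t). At the lowest setting this is 1 − 0.99^204 = 0.87. At every other setting it exceeds 0.95.

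The documents do not give the split of the 102 by arm, so no between-arm bias was calculated. Purely as an illustration, 9 deaths split 3 and 6 would add 0 and 0 patients to listing 14.3.2.

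**The case against.** **Enrolment, not the set definition, is the cause.** Protocol section 4.1 admits only patients who come for the annual visit and sign a separate consent. Section 4.5.3 collects adverse events by asking those who attend. A patient who died earlier never entered this follow-up, and redefining the set would not by itself supply SAE details. This stands, and it is why the non-fatal tables should stay on attendees. It does not justify omitting a death that the study has already recorded.

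**The deaths may be visible elsewhere.** SAP Appendix 1 plans disposition and discontinuation tables in 14.1 and a listing of discontinued patients with reasons in 16.2.1.x. SAP section 6.3.2 presents summaries by treatment group, and section 6.3.3 sorts listings by treatment group. A reader could probably recover deaths by arm from these. This stands in part. The population label on the two 14.1 tables (all included patients) is not defined, so the dead may or may not be in it. Neither these tables nor the listing is a safety comparison.

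**Consent or baseline data might count as an assessment.** Both appear in protocol Table 1. But someone who died before the visit was not assessed at it, and the SAP does not say otherwise.

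**The magnitude rests on assumed rates.** True. The range is nearly tenfold and does not show that harm occurred. The defect does not depend on the rate, because any such death is excluded.

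**Date and cause of death are not held.** Protocol section 4.3.1 records a reason, not a date or cause. Retrieving more for people who did not consent depends on consent and ethics rules. This stands and limits what the fix can require.

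**Conclusion.** The concern holds on the visible text; parts of the SAP are blacked out, and mortality may be addressed there. Followed exactly, the plan leaves every death between the 3-year visit and a first 5-7-year assessment out of the SAE tables and out of listing 14.3.2. The likely number is about 2 to 19 of 102, or about 9 at 3% a year with visits spread equally. This rests on assumed mortality and on 102 as a proxy for the 3-year Safety Set.

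The consequence is bounded. The safety tables are descriptive, the direction of any imbalance is unknown, and this point does not affect the primary mGFR analysis. It should still be fixed, because a named endpoint is reported for survivors only and the correction is small.

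**What to change.** In SAP section 5 and Appendix 1, section 14.3:

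1. Base listing 14.3.2 on all patients in the 3-year Safety Set, whether or not they attended the 5-7-year visit.
2. Add one table of deaths by randomised arm on the same population, using the death recorded as a reason for no consent (protocol section 4.3.1). Give date, cause and any retransplantation where known, and show the rest as not known.
3. Keep the non-fatal AE/SAE tables and the laboratory, vital signs and ECG summaries on attendees. Adding patients who were never asked about events would dilute the rates.
4. Footnote those tables with the number of non-attenders and the number of deaths per arm.
5. Define the population of the 14.1 disposition and discontinuation tables.

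The cost is SAP wording, one table and footnotes. A count by arm needs no new data, provided the reason for no consent is completed for every member of the 3-year Safety Set. The downside is that date or cause of death will be incomplete for some patients, and retrieving more is possible only as far as consent and ethics rules allow.

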6 STATISTICAL AND ANALYTICAL PLANS

The planned tables and listings are presented in Appendix 1.

6.1 Changes in the Planned Analyses

Minnesota Living with Heart Failure Questionnaire was not included in the study.

6.2 Blind Review

This is an open study, however before data base lock the final decisions of patients to be included in study populations, as defined in Section 5 will be made and documented in the Pre-Analysis Review Form.

6.3 Hypotheses and Statistical Methods

6.3.1 Definitions

Baseline: Visit 6 (week 7-11)

Relative day: The relative day of an event is derived as follows:

Relative day = (Start date)-(Date of first administration of Investigational Medicinal Product (IMP))+1.

For days before the start date, calculate as Relative day = (Start date)-(Date of first administration of IMP).

Age: Date of Informed Consent at SCHEDULE main study-Birthdate

6.3.2 Summary Statistics

Data will be summarised by means of summary statistics. For continuous data, the following summary statistics will be presented: number of observations, mean value, standard deviation, minimum, first quartile, median, third quartile and maximum value. Categorical data will be presented as counts and percentages.

Summary statistics will be presented by treatment group/total and assessment visit, as applicable. Individual patient data will be listed.

6.3.3 Patient Data Listings

Data collected in the Case Report Form (CRF) will generally be listed in Appendix 16.2. CRF check questions [e.g. lab samples taken (Yes/No)] and reminders will not be listed.

Listings will be sorted by treatment group, enrollment number and randomization number.

6.3.4 Demographic and other Baseline Characteristics

Demographic data at baseline will be presented using summary statistics for the safety set and ITT.

6.3.5 Primary Efficacy analysis

The primary efficacy analysis will be based on the ITT population, the analysis will be repeated using the PPS and extended PPS.

Two-sided tests will be performed on the 5% level of significance, and 95% two-sided Confidence Interval (CI) for least square mean will be presented.

The null hypothesis is that there is no difference in the mean of mGFR between the Everolimus arm ($\mu_{\text{Everolimus}}$) and the Control arm (Control) (μ_{Control}) and the alternative hypothesis is that there is a difference between Everolimus and Control at the 5-7-years follow-up visit.

$$H_0: \mu_{\text{Everolimus}} - \mu_{\text{Control}} = 0$$

[figure not shown]
$$H_1: \mu_{\text{Everolimus}} - \mu_{\text{Control}} \neq 0$$

The above between-group comparisons will be performed using an Analysis of Covariance (ANCOVA) with study treatment (Everolimus, Control) and randomization strata (mGFR above/below 60 mL/min and have/not have mechanical assist device) as classification variables. In addition, the mGFR values at baseline will be used as covariate.

All mGFR data, observed values as well as change from baseline, will be presented using summary statistics by treatment group and in total. This presentation will be given for both observed values only as well as imputed mGFR, see Section 6.6.

6.3.6 Secondary Efficacy Analyses

- The analysis of the IVUS-data will not be performed by [REDACTED]
- Echocardiography variables LVEDD, LVESD, LVEF and FF will be presented by summary statistics for observed values by treatment group and in total.
- Quality of life:
 - The eight SF-36 dimensions together with Physical Health Summary and Mental Health Summary will be presented by summary statistics for observed values and change from pre-transplantation by treatment group and in total.
 - The EQ-5D index and the VAS-scale will be presented by summary statistics for observed values and change from pre-transplantation by treatment group and in total.
 - BDI form will be presented by two shift tables. The first one showing the number of patients who changed from normal, mild, moderate or severe at pre-transplantation to normal, mild, moderate or severe at each post-transplantation time of assessment by treatment group and in total. The second will show the number of patients who changed from normal, mild, moderate/severe at pre-transplantation to normal, mild, moderate/ severe at each post-transplantation time of assessment by treatment group and in total.

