This protocol is written to describe the procedures for a single 5, 6 or 7 year follow-up control visit of patients that participated in the 12-month SCHEDULE-study and the following 3-year follow-up examination/visit. The aim of this 5 to 7-year follow-up visit is to examine the effect of long term treatment, i.e. 5, 6 or 7 years, with early initiation of everolimus (Certican®) and early elimination of cyclosporine (CsA), compared to standard immunosuppressive regimen including CsA, on renal and heart function. During the time period of this follow-up examinations this visit will be performed as part of a routine annual visit 5, 6 or 7 years since transplantation (and inclusion in the original SCHEDULE study).

PROTOCOL FOR THE 5 TO 7-YEAR FOLLOW-UP EXAMINATION

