2 STUDY OBJECTIVES

Purpose

To evaluate, in *de novo* heart transplant recipients, whether early initiation of everolimus and early elimination of cyclosporine (CsA), compared to standard immunosuppressive regimen including CsA can improve long-term renal function and slow down the progression of Cardiac Allograft Vasculopathy (CAV).

Aim

The major aim of this extension study is to evaluate the long-term (i.e. 5 to 7 years) effect of early initiation of everolimus and early elimination of CsA compared to standard immunosuppressive regimen including CsA on primary and secondary endpoints investigated in the SCHEDULE main study.

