6.4 Level of Significance, Multiple Comparisons and Multiplicity

The primary comparison will be performed on one single variable at one single occasion no adjustment of the statistical significance level will be made for multiple analyses. [REDACTED]

[figure not shown]

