14.2 EFFICACY DATA

Primary (ITT [PPS, extended PPS])

mGFR (mL/min/1.73m²) 5-7-years Follow-Up (ANCOVA, CI, p-value, summary statistics including imputed values (or if not imputed the observed value will be used) and changes from baseline by treatment group and total)

Secondary (ITT)

- *IVUS – Not done by [REDACTED]*
- Echocardiography (the variables LVEDD, LVESD, LVEF and FF, summary statistics for observed values by treatment group and total)
- Quality of life:
 - SF-36: Physical Health Summary, Mental Health Summary, Physical Functioning, Role Physical, Bodily Pain, General Health, Vitality, Social Functioning, Role Emotional, Mental Health (summary statistics for observed values and change from pre-transplantation by treatment group and total)
 - EQ-5D index and VAS (summary statistics for observed values and change from pre-transplantation by treatment group and total)
 - BDI form (shift tables)

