14.3.9 Concomitant Medication at 5-7-years Follow-Up Visit

7.2 Graphs (Section 14.2-14.3 in ICH E3)

None

7.3 Listings of Individual Patient Data and other Information to be Produced for the Clinical Study Report (Sections 16.1 and 16.2 according to ICH E3)

(Listing numbers refer to Appendix number in ICH E3. CRF check questions/reminders will not be listed.)

- 16.1.7 Randomisation Scheme (*Copy of List, included in CSR for 12 Months*)
- 16.2.1.x Discontinued Patients, Reason for Discontinuation (from 3-years follow-up to 5-7 follow-up visit)
- 16.2.1.x Visit Dates and Other Important Dates
- 16.2.1.x *Study Termination – Not Applicable*
- 16.2.2 Protocol Deviations
- 16.2.3.x Patients Excluded from the Efficacy Analysis (Evaluable, Reason for Evaluable Classification)
- 16.2.3.x Treatment Allocation and Evaluable for All Patients
- 16.2.4.x Demographic Data
- 16.2.4.x Inclusion Criteria Not Met and Exclusion Criteria Met
- 16.2.5 Compliance and/or Drug Concentration Data
 - Immunosuppressive Medications
 - Immunosuppressive Level
- 16.2.6 Individual Efficacy Response Data
 - mGFR (mL/min/1.73m²)
 - IVUS (performed yes/no and date)
 - Echocardiography

- SF-36
- EQ-5D
- BDI form
- [REDACTED]

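### Echocardiography and quality of life fall under a comparative aim, but the readable SAP pre-specifies no between-arm difference with its precision for them

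*SAP*

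**What the plan says.** The statements of purpose differ in breadth.

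- The Aim in SAP 2, repeated in Protocol 2, is to evaluate the long-term effect of the everolimus regimen "compared to standard immunosuppressive regimen including CsA on primary and secondary endpoints investigated in the SCHEDULE main study".
- The protocol's opening description of the visit states the effect to be examined as "compared to standard immunosuppressive regimen including CsA, on renal and heart function".
- The Purpose (Protocol 1.2, SAP 2) and the last paragraph of Protocol 1.1 are narrower. They name only renal function and CAV.

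Echocardiography and quality of life are listed as secondary endpoints in Protocol 2 and SAP 3.2. SAP 5 sets the population: "The ITT is considered as the primary analysis dataset, and will be used for the primary, secondary" variables, with the rest of that phrase redacted.

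On analysis, SAP 6.3.6 reads: "Echocardiography variables LVEDD, LVESD, LVEF and FF will be presented by summary statistics for observed values by treatment group and in total". SF-36 and EQ-5D get the same summaries plus change from pre-transplantation. BDI gets two shift tables by treatment group and in total. Table list 14.2 repeats this for echocardiography: "Echocardiography (the variables LVEDD, LVESD, LVEF and FF, summary statistics for observed values by treatment group and total".

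The descriptive approach is stated in Protocol 4.4: "In general data will be summarised by means of summary statistics". SAP 6.4 adds: "The primary comparison will be performed on one single variable at one single occasion", which concerns mGFR.

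**The concern.** An aim to evaluate one regimen against another on an endpoint is answered by an estimated difference between arms with a measure of its uncertainty. The readable plan gives results arm by arm and stops there. In an open-label trial with four echocardiography variables and three questionnaires, the contrast, the covariates and the handling of missing pre-transplant scores would then be chosen after the arm-level results are visible. BDI is the thinnest case. SAP 3.2 defines a total score from 0 to 63, but the planned tables show only bands, so the total reaches the reader, if at all, through the individual listings ("16.2.6 Individual Efficacy Response Data").

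**Working it through.** **Text check.** The documents give no sample size, SD or target difference for these endpoints (SAP 4.2 declares sample size not applicable), so there is no figure of the plan to reproduce. The planned output by endpoint is:

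| Endpoint | Planned output (SAP 6.3.6, table list 14.2) | Between-arm difference with CI |
|---|---|---|
| mGFR | ANCOVA, CI, p-value, summaries | yes |
| LVEDD, LVESD, LVEF, FF | summaries of observed values by arm | no |
| SF-36, EQ-5D index, VAS | summaries of observed values and change by arm | no |
| BDI | two shift tables by arm | no |

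SAP 6.3.2 defines the summaries as n, mean, SD, minimum, quartiles, median and maximum. No difference, standard error, CI or test is listed. The ANCOVA in SAP 6.3.5 and 6.5 is tied to mGFR by its hypothesis and by its baseline mGFR covariate.

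**Size of the intervals if they were added.** Documented input: 102 patients attended the 3-year visit, and completing it is an inclusion criterion, so 102 is a ceiling. Assumptions: N analysed from 60 to 102, equal arms, and correlation r of 0.1 to 0.5 between pre-transplant and 5-7-year quality-of-life scores. Half-widths are in SD units.

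1. Unadjusted: t(0.975, N−2) × √(4/N).
   - N=60: 2.002 × 0.258 = 0.517
   - N=80: 0.445
   - N=102: 1.984 × 0.198 = 0.393

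   With a 40/60 split the results are 0.527 (N=60) and 0.401 (N=102).
2. Strata only (four strata): t(0.975, N−5) × √(4/N) = 0.517 (N=60) and 0.393 (N=102).
3. ANCOVA with strata and pre-transplant score: t(0.975, N−6) × √(4/N) × √(1−r²).

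| r | N=60 | N=102 |
|---|---|---|
| 0.1 | 0.515 | 0.391 |
| 0.3 | 0.494 | 0.375 |
| 0.5 | 0.448 | 0.340 |

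The gain in precision from adjustment is small at low r. The main gain is that the estimate is fixed in advance.

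**Missing pre-transplant scores.** This step concerns the proposed model, not the plan. Take r=0.3 and 20% of pre-transplant scores missing at random (assumed).

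- Complete-case ANCOVA, with n = 0.8N in formula 3: 0.556 (N=60) and 0.421 (N=102). Both are wider than no adjustment.
- Covariate imputed with the overall mean of both arms, t(0.975, N−6) × √(4/N) × √(1−0.8r²): 0.499 and 0.379.

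A rule that keeps these patients is therefore needed.

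**The case against.** The strongest reply is that description was a deliberate and consistent choice. Protocol 4.4 sets it as the general approach and gives a hypothesis and model for mGFR only, and SAP 6.3.6, 6.4 and 14.2 follow. Confining inference to one variable in a follow-up without a sample-size calculation is legitimate. The Purpose and Protocol 1.1 do not name echocardiography or quality of life, and results set side by side by arm are a comparison of a kind. All of this stands, and it limits the point to an improvement.

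A reader might infer more than the documents support:

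- *That the SAP drops a promised analysis.* Protocol 4.4 does speak of testing and of CIs to estimate effects, but that sentence sits between the primary-analysis statement and the mGFR hypothesis, and no other model is given.
- *That no comparison can be recovered.* From n, mean and SD by arm, a crude difference and CI can be derived for echocardiography, SF-36 and EQ-5D. The margins of the BDI shift tables give band proportions by arm for patients with both assessments. What is missing is advance choice of the contrast and adjustment, and the BDI total by arm.
- *That redaction hides the analysis, or that IVUS and adverse events share the gap.* The echocardiography and quality-of-life lines in SAP 6.3.6 and 14.2 are fully readable. IVUS is analysed elsewhere, adverse events are a safety endpoint in SAP 3.3, and nothing is inferred from redacted text or the absent section 6.3.7.

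**Conclusion.** The point holds as a mismatch between the broad Aim and the readable plan: none of the echocardiography or quality-of-life analyses has a pre-specified between-arm difference with its precision. The primary mGFR comparison is unaffected. Added intervals would have half-widths of about 0.4 to 0.5 SD, so they would show how uncertain the differences are rather than settle them. That range rests on an assumed N of 60 to 102 and equal arms; the adjusted figures also rest on the assumed r. Any such result describes only patients who completed the 3-year visit and were assessed at 5-7 years. The change is worth making because it is cheap and lets the study answer its stated Aim, not because the present plan is invalid.

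**What to change.** **SAP 6.3.6 and table list 14.2.** Add the between-arm difference with 95% CI at the 5-7-year visit for:

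- SF-36 Physical and Mental Health Summary, EQ-5D index, VAS and BDI total score (five), from an ANCOVA with treatment, randomisation strata and pre-transplant score, keeping patients whose pre-transplant score is missing;
- LVEF, FF, LVEDD and LVESD (four), with treatment and strata only. The early echocardiograms listed in SAP 3.2 (week 2, and baseline at week 7-11) fall in period 1, apparently after randomised treatment began. The documents do not give the day of first dose, and the primary model does adjust for week 7-11 mGFR, so the SAP should state the reason for the difference.

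Tabulate the BDI total score by arm. Keep all planned descriptive tables, and leave the eight SF-36 dimensions descriptive to limit the number of intervals.

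**Matching edits.** In 6.4, keep the single-comparison wording for the primary test and state that the nine intervals are supportive and not multiplicity-controlled. In 6.5, add the covariates. In 6.6, add the rule for missing pre-transplant scores, for example the overall mean of both arms.

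**Cost.** SAP wording in these places, nine standard models and one BDI table, all on data already collected. The downside is nine fairly wide intervals without multiplicity control, describing attenders only. If the sponsor prefers description only, saying in SAP 2 and 6.3.6 that these endpoints support no comparative conclusion would remove the mismatch but give no estimate.
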